#### 10.9. Final Visit

A final meeting with the participant will be held approximately one week after the last measurement visit. The HRA will pick up all of the issued equipment and return to L2S2 for cleaning.

A final report will be issued to all participants within three months of the end of Phase 2.

The exact interval between measurements will be data driven, set by monitoring the returned data.

#### 10.10. Common to all Visits

The following procedures will be checked at the start of each visit by the HCA:

- eligibility check confirm nothing has changed e.g. mental capacity
- assessment of outcome measures
- assessments of safety
- assessments of compliance with the study protocol
- general health and wellbeing of the patient

## 10.11. Sample Handling

No samples will be taken from participants in this study.

Self-entered data or data collected by Bluetooth connected devices is described separately.

## 10.12. Early Discontinuation/Withdrawal of Participants

During the course of the study a participant may choose to withdraw early from the study treatment at any time. This may happen for several reasons, including but not limited to:

- The occurrence of what the participant perceives as an intolerable adverse event
- Inability to comply with study procedures
- Participant decision

Participants may choose to stop the study assessments.

Participants may also withdraw their consent, meaning that they wish to withdraw from the study completely.

 Participants may withdraw from active participation but allow the study team to continue to access their medical records and any relevant hospital data that is recorded as part of routine standard of care.

2) Participants can withdraw from the study but permit data and samples obtained up until the point of withdrawal to be retained for use in the study analysis. No further data would be collected after withdrawal.

In addition, the Investigator may discontinue a participant from the study treatment at any time if the Investigator considers it necessary for any reason including, but not limited to:

- Ineligibility (either arising during the study or retrospectively having been overlooked at screening)
- Significant protocol deviation
- Admission to hospital care
- Clinical decision

Following a complete withdrawal, confirmation will be sent to the participant confirming destruction of all personal data.

All data obtained from registered/enrolled participants will be analysed. Withdrawal from the study may result in exclusion of the data for that participant from certain analyses.

If participants leave the study for any reason a substitute will be sought to maintain study numbers to provide as high a volume of data as possible to train the machine learning.

The type of withdrawal and reason for withdrawal will be recorded in the Case Report Form (CRF).

If the participant is withdrawn due to an adverse event, the Investigator will arrange for follow-up visits or telephone calls until the adverse event has resolved or stabilised.

## 10.13. Definition of End of Study

The end of the study will be when the final report and recommendations are presented to the CCG in October/November 2020. The data governance, quality management, and archiving will continue for three further years when the data will be destroyed.

## 11. SAFETY REPORTING

This is a non-interventional study. It uses CE approved medical devices together with mobile phone technology and a digital watch. No serious adverse events are predicted; therefore, safety reporting is not applicable.

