## 5.4. Risks

L2S2 perform risk analyses to ISO 14971 as part of the company ISO 13485 Quality Management System (QMS). Risks for this project are listed below:

001 Risk: Cross Infection between patients

Hazard: Bacteria, spores and viruses could be transferred by a device if reused

Hazardous Situation: Inadequate cleaning / disinfection / sterilization

Harm: Pathogens could be transferred between patients

Likelihood: Frequent

Severity: Serious

Risk Assessment: Serious

Mitigation: All devices will have a record entry in the master device database that will show cleaning status and allow cleaning process to be tracked.

Cleaning / Disinfection / Sterilisation will be performed to formal procedures and tracked

Devices that enter or contact mucous membranes will either be single use or will be returned to the company for formal cleaning between each reuse.

Cleaning processes will be audited once per month.

Residual Risk: Acceptable

002 Risk: Contact Dermatitis

Hazard: Patient's skin reacts with surfaces of any of the medical devices

Hazardous Situation: Allergic or rash reaction happens after wearing / touching the devices

Harm: Discomfort, rash or swelling requiring intervention

Likelihood: Rare

Severity: Minor

Risk Assessment: Reasonable

Mitigation: Patients will be asked if they have a history of adverse effects from any contact materials as part of the study inclusion criteria and throughout the study. The HCAs will check the patients at each visit, and to minimise any effects, the device will be withdrawn from the patient if any adverse effects are detected.

Residual Risk: Acceptable

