### 12.3. Stopping rules

The CCG has the final decision to end the trial. This is a non-interventional, observational study and the data will not be analysed until the study is complete, and therefore other than the CCG deciding that the study is not being managed correctly, the study will proceed to the planned end.

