#### 27. Appendix E COVID-19 Procedures

Specific COVID-19 procedures have been added to the monitoring app and the care home staff research assistant's SOP.

Phase 1 of the trial was suspended because of the onset of COVID-19 in the UK. It was clear in February 2020 that visiting care homes would be unsafe and the UK was put into lockdown by the government on 23 March to attempt to limit the spread of coronavirus.

It appears that the government will gradually lift lockdown rules from June 2020 but it will be necessary to continue shielding of vulnerable participants for the foreseeable future. The study cohort is focussed on the over 65s with multiple co-morbidities and this group will be particularly susceptible to harm by COVID-19. It would not be possible to visit care homes under the government guidelines that state that care homes should restrict all non-essential healthcare visits.

The trial protocol has been revised to avoid the need for physical contact with the care homes and participants.

The Reassure app used to collect data in this trial has been updated to include secure video conferencing and safety features that make it possible to conduct the trial remotely and yet still obtain reliable data. The app is already in use in NHS hospitals to allow remote monitoring of participants at home during COVID-19.

Before COVID-19 it was intended that staff in some care homes would collect the participant data. Now only care homes that will allow their staff to collect data will be included in the trial. It is proposed that the care home staff will receive training via the app video link to enable them to use the devices safely and achieve good data quality.

The video will not be used for or with participants, only for staff assistance and training.

Each time it is used, the opening screen of the app will assess whether the participant is displaying the symptoms of COVID-19 infection.

It does this by requiring the staff member to follow an on-screen protocol as follows:

- At the start of each shift the staff member shall record their own temperature and answer COVID symptoms questions. If COVID is suspected, the app will prevent further use by that staff member until a negative result from a formal COVID-19 test is entered or until seven days have passed from the last symptoms. If the staff member is not suspected of having COVID0-19 the app continues as before.

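### Section 11 rules out safety reporting although the protocol rates one hazard serious before mitigation and follows up adverse events, so device- or visit-related harm without a breach has no planned reporting route or summary

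*Protocol*

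**What the plan says.** Section 11 describes the study as non-interventional, with CE-approved devices, phones and a watch, and concludes: "No serious adverse events are predicted; therefore, safety reporting is not applicable".

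Other sections expect that harm may occur and look for it:

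- **5.4 Risks.** Risk 001 is cross infection by reused devices: "Harm: Pathogens could be transferred between patients". Likelihood is Frequent, severity Serious, and the overall entry is "Risk Assessment: Serious". Cleaning controls with a monthly audit bring the residual risk to Acceptable. Risk 002, contact dermatitis, is Rare and Minor, with "Risk Assessment: Reasonable", and its residual risk is also Acceptable.
- **7.1 Visit Plan.** In Phase 2, follow-up visits (made on request) include confirming that the participant has no adverse effects, bodily or mental.
- **10.4 Device safety.** Skin is checked at each Phase 1 visit. Phase 2 participants are told to report skin reactions and other problems to the research team, and a device that causes an issue is taken back.
- **10.10.** A safety assessment is among the checks at the start of every visit.
- **10.12.** An intolerable adverse event is a listed reason for withdrawal, the reason goes in the CRF, and "If the participant is withdrawn due to an adverse event, the Investigator will arrange for follow-up visits or telephone calls" until the event settles.

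On decisions, 12.2 describes an interim report on the first 100 patients covering device and condition performance and correlations. L2S2 and the CCG jointly decide when Phase 2 starts. Section 12.3 says "The CCG has the final decision to end the trial", and adds that "other than the CCG deciding that the study is not being managed correctly, the study will proceed to the planned end". Section 18 provides a route to the sponsor, and if appropriate to the ethics committee and NHS host, for serious breaches of the protocol or of GCP.

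**The concern.** The inference in section 11 does not hold. That no serious event is predicted is no reason to have no reporting rule, because reporting exists largely to catch what was not predicted. The statement is also a positive rule, not a detail left for another document, and it conflicts with the protocol's own risk register, visit checks and adverse-event follow-up.

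At stake is the information available when the study moves from up to 100 care home residents, measured by staff, to 500 participants, many measuring themselves at home. If staff see skin reactions, distress or suspected device-linked infections in Phase 1, the protocol does not say who is told, who counts them, or that the count is before L2S2 and the CCG when they decide on Phase 2. For the same reason, the final report would have no planned tabulation against which to test the claim in 10.4 that the risk to participants is extremely low.

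**Working it through.** There is no figure in the protocol to reproduce, so the check is to follow different kinds of harm through the sections and see where each one ends.

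1. **Harm caused by a breach, such as failed cleaning.** Section 18 applies if the breach is likely to affect participants' safety to a significant degree. The sponsor is contacted within 1 working day and, if appropriate, the ethics committee and NHS host within seven calendar days. The CCG could also treat it as mismanagement under 12.3. A route exists.
2. **Harm that leads to withdrawal.** Section 10.12 records the reason in the CRF and follows the event up. The individual is covered, but no onward report or summary is named.
3. **Severe worsening seen by study staff and unknown to the medical team.** Section 19.4 has it discussed with the participant's care team. No route to the sponsor is named.
4. **Suspected COVID-19.** Appendix E screens for symptoms each time the app is used, temporarily excludes suspected cases, reserves separate devices for confirmed ones and logs all actions. This infection is watched for.
5. **A skin reaction, distress, or another infection after cleaning done to procedure, in a participant who stays in.** Section 10.4 takes the device back if there is an issue. Sections 13.1 and 13.3 have data gathered at visits stored in the L2S2 system. Section 11 says reporting does not apply, section 18 does not apply because nothing was breached, 12.2 lists no safety item, and 12.3 names no safety ground.

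The gap is therefore the fifth case, and the absence of any planned count across all five.

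**Illustration of size.** The protocol gives no rate of device- or visit-related harm, so the rates p below are assumptions. The number of participants, n = 100, is the Phase 1 maximum.

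Chance of at least one event = 1 − (1 − p)^100:

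| Assumed p | Calculation | Chance of at least one |
|---|---|---|
| 0.5% | 1 − 0.995^100 | 39% |
| 1% | 1 − 0.99^100 | 63% |
| 2% | 1 − 0.98^100 | 87% |
| 5% | 1 − 0.95^100 | 99% |

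If all such events were recorded and counted and none occurred in 100, the exact one-sided 95% upper bound on the rate would be 1 − 0.05^(1/100) = 0.0295, about 3.0%. With none in 500 it would be 1 − 0.05^(1/500) = 0.0060, about 0.6%. Such bounds need a defined event and a systematic count, and the protocol plans neither.

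**The case against.** The case on the other side is substantial. The study is observational and uses CE-marked devices within their registered scope. Only one risk is rated Serious, before mitigation, and both residual risks are Acceptable. Harm is handled participant by participant (10.4, 10.12, 19.4). Section 18 carries breach-related harm to the sponsor and ethics committee, and failed cleaning is an obvious way for the one serious risk to materialise. A monitoring plan, a risk assessment and SOPs are mentioned but not shown, and they may say more.

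Most of this stands, and it rules out several stronger readings that a reader might infer:

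- *That the protocol names several serious risks.* It names one, before mitigation. Dermatitis is rated minor.
- *That harm cannot influence Phase 2 or stop the study.* The contents given for the interim report in 12.2 are not stated to be exhaustive, the Phase 2 decision has no criteria that exclude safety, and the CCG keeps the final decision to end the trial.
- *That safety observations are not collected.* Section 11 removes reporting, not recording. Sections 10.10, 13.1 and 13.3 point to visit data being stored.
- *That 12.3 is contradicted by Appendix E, which says* "Phase 1 of the trial was suspended because of the onset of COVID-19 in the UK". Section 12.3 is about whether the study reaches its planned end. A temporary suspension in a pandemic is a different matter, and it shows that a pause was possible in practice.

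None of this supplies a reporting route or a summary for related harm without a breach. Nor can documents not shown here cure a sentence in the protocol that says reporting does not apply.

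**Conclusion.** The point holds in limited form. Section 11 is inconsistent with 5.4, 7.1, 10.4, 10.10 and 10.12. As written, device- or procedure-related harm that involves no breach, in a participant who remains in the study, has no planned reporting route or aggregate summary. It is neither listed for the interim report nor named in the stopping rule. The defect is the lack of a planned route. It does not prove that harm would go unnoticed or could not be acted on.

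The size cannot be taken from the protocol. At assumed rates of 1% to 5%, Phase 1 would more likely than not produce at least one such event (63% to 99%); at 0.5% it would be 39%. These rates are illustrative only. The prediction analysis is not affected. The change should be made because it concerns participant safety and the evidence behind the step to 500, but it does not call the whole design into question.

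**What to change.** 1. **Section 11.** Replace the statement that reporting does not apply with a limited rule, reconciled with 5.4, 10.10 and 10.12. Adverse events judged related to a device, a measurement or a study visit are recorded in the existing CRF, whether or not the participant withdraws. Serious ones are reported to the sponsor and, where appropriate, to the ethics committee, on timelines that the sponsor sets. Section 18 is an available model for those timelines.
2. **Scope.** State that expected admissions and exacerbations remain outcome data and are not reported under this rule.
3. **Section 12.2.** Add a count of these events, with the number of participants exposed, to the interim report.
4. **Section 12.3.** State that safety information is considered in decisions to pause or end the study. The criteria are for the sponsor to set.

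The cost is a short amendment, one CRF form and modest reporting work, kept small by the restriction to related events.

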#### 12. STATISTICS AND ANALYSIS

## 12.1. Statistical Analysis

Studies to measure interventions are designed using power calculations that minimise the risk of not finding a difference between treatments if one exists (a type II error).

In a purely observational study, such calculations are less relevant, but the study design still needs to provide assurance that sufficient data will be collected to but for this study.

This is mainly achieved by ensuring that the target population has a high event frequency of the index condition — in this case deterioration of healthcare such that hospital admission would be necessary. The mean time of residence for a patient in nursing home care is approximately 15 months, but with half the residents dying in the first six months of residence.

https://www.geripal.org/2010/08/length-of-stay-in-nursing-homes-at-end.html?m=1

Following the protocol described below, a cohort of elderly people (>65 years) living independently and in care/nursing homes, with

- a moderate or high degree of frailty,
- comorbidities as defined in the appendix using standardised NHS list
- a history of regular NHS activity will be identified.

Stage 1 of data collection will feature a universal monitoring plan across for nursing home residents and, following analysis, Stage 2 of data collection will ensure measurements are collected with frequency and using devices appropriate to the needs of different participants by tailoring the frequency and type of monitoring to the needs of the condition and patient.

To provide assurance that the sample size is likely to provide sufficient event frequency, a power calculation was performed (Jones et al. 2003).

Data provided by the West Essex CCG was used to explore different incidence rates of index episodes of health deterioration requiring NHS treatment in the target population as defined above.

As 50% of the nursing home population is likely to die within six months of admission, the recruitment of existing nursing home patients means event prevalence rates of 55% is a conservative estimate.

The lowest acceptable sensitivity of the algorithm was assumed to be 85% (SN) and the lowest acceptable specificity – 80% (SP). A confidence interval of 5% (W) was selected. The required sample size can be determined via the sensitivity or the specificity limit, depending on priorities:

$$N(SN) = \frac{TP + FN}{P} = 1.96^2 * \frac{(SN(1 - SN))}{W^2}$$

$$N(SP) = \frac{FP + TN}{(1 - P)} = 1.96^2 * \frac{(SP(1 - SP))}{W^2}$$

		Incid	dence of h	ealth issue		
	0.3	0.35	0.4	0.45	0.5	0.55
N(SN)	653	560	490	435	392	356
N(SP)	280	301	327	356	392	435

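### The specificity sample sizes in Protocol section 12.1 do not follow from the stated 80% specificity; they reproduce only with 85%, and each is about 20% too low if 80% stands

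*Protocol*

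**What the plan says.** Protocol section 12.1 justifies the study size partly by a precision calculation for the sensitivity and specificity of the prediction algorithm.

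- Accuracy limits: "The lowest acceptable sensitivity of the algorithm was assumed to be 85% (SN) and the lowest acceptable specificity – 80% (SP").
- Precision: "A confidence interval of 5% (W) was selected". The formulas use 1.96 as the multiplier.
- Sensitivity row, for incidence 0.30, 0.35, 0.40, 0.45, 0.50 and 0.55: "N(SN) 653 560 490 435 392 356".
- Specificity row, for the same incidences: "N(SP) 280 301 327 356 392 435".
- Choice of row: the section allows the size to be set by either the sensitivity or the specificity limit, according to which matters more. It does not name the priority.
- Incidence: the text argues that "event prevalence rates of 55% is a conservative estimate", while the Stage I and Stage II projection tables in the same section use 35% throughout.

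The planned size is 500 in Phase 2 (Synopsis and section 5.2). The closing sentence of section 12.1 gives 100 for the first stage and 400 for the main stage, and the Stage II table starts with 500.

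**The concern.** The two printed rows mirror each other. Both are 392 at incidence 0.50, and 435 and 356 change places between 0.45 and 0.55. With a common W and multiplier, that happens only if the same accuracy value lies behind both rows. The text gives two different values, 85% and 80%, so at least one row, or the text, must be wrong.

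The specificity row tells a reader how many participants are needed to estimate the false-alarm side of the algorithm to the chosen precision. If the row is too low, 500 looks comfortably sufficient for specificity at 55%, the incidence the text argues for, when on the stated inputs it is not.

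**Working it through.** **Inputs**, all from Protocol section 12.1: SN = 0.85, SP = 0.80, W = 0.05, multiplier 1.96, incidence P = 0.30 to 0.55.

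**Formulas**

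- People with an event: 1.96² × SN(1 − SN) / W². Then N(SN) is this number divided by P.
- People without an event: 1.96² × SP(1 − SP) / W². Then N(SP) is this number divided by (1 − P).

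**Step 1: reproduce the sensitivity row.** 1.96² × 0.85 × 0.15 / 0.0025 = 195.92. Dividing by P gives 653.1, 559.8, 489.8, 435.4, 391.8 and 356.2. All six printed values follow by rounding to the nearest integer. This confirms the formula, the use of W as a half-width, and the rounding rule.

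**Step 2: specificity row with the stated 80%.** 1.96² × 0.80 × 0.20 / 0.0025 = 245.86. Divide by (1 − P), and compare with the same calculation using 0.85 (195.92):

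| P | Printed N(SP) | With SP = 0.80 | With 0.85 |
|---|---|---|---|
| 0.30 | 280 | 351.2 | 279.9 |
| 0.35 | 301 | 378.2 | 301.4 |
| 0.40 | 327 | 409.8 | 326.5 |
| 0.45 | 356 | 447.0 | 356.2 |
| 0.50 | 392 | 491.7 | 391.8 |
| 0.55 | 435 | 546.4 | 435.4 |

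No printed value matches 80%; all six match 85%.

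**Step 3: other explanations, keeping SP = 0.80.** A multiplier of 1.645 gives 247 to 385. A multiplier of 2 gives 366 to 569. Reading W as a full width (half-width 0.025) gives 1405 to 2185. None gives the printed row.

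**Step 4: size of the discrepancy.** 0.1275 / 0.16 = 0.797, so each printed value is 20.3% below the value for 80%. Put the other way, the value for 80% is 25.5% above the printed one.

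**Step 5: comparison with 500.** Among the tabulated incidences, the correction moves N(SP) past 500 only at 0.55 (435 becomes 546). At 0.50 it is 492, still within 500.

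**Step 6: precision that 500 gives**, as 95% half-widths in percentage points:

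- P = 0.35 (175 with an event, 325 without): sensitivity 1.96 × √(0.1275/175) = 5.3; specificity 1.96 × √(0.16/325) = 4.3.
- P = 0.55 (275 with an event, 225 without): sensitivity 1.96 × √(0.1275/275) = 4.2; specificity 1.96 × √(0.16/225) = 5.2.

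**The case against.** The strongest reply is that little depends on this row. The section lets either limit set the size. After correction, 500 still meets one limit at every tabulated incidence: specificity at 0.30 to 0.40 (351 to 410) and sensitivity at 0.40 to 0.55 (490 down to 356). The projections run at 35%, where the corrected specificity requirement of 378 is covered. The section's conclusion claims only reasonable assurance of enough index events in an exploratory study, not ±5 points on both measures. All of that stands and limits the weight of the point. It does not make the printed row agree with its stated inputs.

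Several stronger readings are tempting, but the document does not support them:

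- *That 500 is too small because it misses one target at both 35% and 55%.* This requires both limits at once, which the section does not. The sensitivity requirement of 560 at 35% is already printed correctly and owes nothing to this error.
- *That the study size rests on this table alone.* The section says its assurance comes mainly from choosing a population with frequent events, and it projects episode counts as well.
- *That 492 at 50% incidence fails because only 464 remain after the first month's dropout.* The section does not adopt 50%. Its table keeps the cumulative number of patients at 500, and section 10.12 provides for substitutes. Taking 464 as the number analysed would be an added assumption.
- *That the table is certainly the wrong side.* The document does not show whether the 80% in the text or the 85% behind the row is the slip.

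**Conclusion.** The text and the table of section 12.1 contradict each other on specificity. This follows from the section's own inputs and needs no outside figure. If 80% is intended, the specificity row should read 351, 378, 410, 447, 492, 546, and every printed value is about 20% too low. These figures use nearest-integer rounding, as the table does; rounding up gives 352, 379, 410, 448, 492, 547. If 85% is intended, the row is right and the stated specificity is wrong.

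Under the 80% reading the consequence is confined to 55% incidence, the value the text argues for. The requirement there is 546 rather than 435, and 500 gives specificity to about ±5.2 points instead of ±5.0. The half-widths assume that all 500 contribute and that the true accuracy equals the stated limits. This should be corrected, but it does not call for a larger study.

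**What to change.** Decide which specificity was intended and make the text and the table agree.

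- If 80% stands: replace the N(SP) row with 351, 378, 410, 447, 492, 546, and state the precision that 500 participants give at the two incidences the section uses. At 35% this is about ±5.3 points for sensitivity and ±4.3 for specificity; at 55%, about ±4.2 and ±5.2.
- If 85% was intended: correct the stated specificity and leave the row as it is.

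In either case, show the division by P and by (1 − P) on the right-hand side of the two formulas. As they read now, those expressions give the number with or without an event, not the total. The table already applies the division, so no figure changes, and the omission may be an artefact of how the equations were read from the PDF.

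The cost is an edit to Protocol section 12.1. No extra participants are needed, and enrolment and analysis do not change.

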	# unique patients											
Stage II		nursing/ indep. care living						# unique patient non- episode		# unique patient episode		
incidence of an episode	month	new	old	new	old	total	dropout rate	cumulative patients	month	cum	month	cum
35%	1	400		100		500	36	500	325	325	175	175
35%	2		371		93	464	33	500	302	627	162	337
35%	3		344		86	430	31	500	280	907	151	488

Therefore for this observational / exploratory study, the study design and numbers proposed (100 for the first stage and 400 for the main stage) provide reasonable assurance that a sufficient number of index events will occur in the target population.

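### Section 12.1 sets minimums for both sensitivity and specificity but sizes the study on either one without saying which; with both required, 500 falls short at the 35% and 55% incidences the protocol itself uses

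*Protocol*

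**What the plan says.** Section 12.1 of the protocol sets two performance limits together: "The lowest acceptable sensitivity of the algorithm was assumed to be 85% (SN) and the lowest acceptable specificity", the second given as 80%. A single precision applies to both: "A confidence interval of 5% (W) was selected". The next sentence makes the sizing a choice: "The required sample size can be determined via the sensitivity or the specificity limit, depending on priorities". A table follows with N(SN) and N(SP) for incidences 0.30 to 0.55.

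Two incidences are then in use. The text says that "event prevalence rates of 55% is a conservative estimate", while the Stage I and Stage II accrual tables work at 35%. The section closes by saying that the numbers "provide reasonable assurance that a sufficient number of index events will occur in the target population". Neither that sentence nor any other says which row of the table governs.

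**The concern.** A value described as the lowest acceptable is a requirement. When two such values are stated with one precision, a study sized for only one of them does not deliver the stated precision on the other. N(SN) falls as incidence rises and N(SP) rises, so the choice of row matters most at the ends of the grid. The two incidences the protocol relies on, 35% and 55%, lie towards opposite ends.

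What is at stake is what a reader may take from the sample-size section. It appears to support 5-point precision on both measures. Whether 500 patients give that depends on a priority that is not stated and on an incidence that is not settled.

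**Working it through.** **Inputs.** Section 12.1: SN = 0.85, SP = 0.80, W = 0.05, multiplier 1.96. Phase 2 size of 500: Synopsis, section 5.2 and the Stage II table. Incidence P: 0.35 (accrual tables) and 0.55 (text of 12.1).

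**Formulas.** The printed expressions give the table when the right-hand side is read as the number of cases (TP + FN) or non-cases (FP + TN) and then divided by P or 1 − P. W enters as a half-width.

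- Cases needed: 1.96² × 0.85 × 0.15 / 0.05² = 195.9, so N(SN) = 195.9 / P.
- Non-cases needed: 1.96² × 0.80 × 0.20 / 0.05² = 245.9, so N(SP) = 245.9 / (1 − P).

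**Reproducing the printed table.** The N(SN) row reproduces in all six cells. The N(SP) row does not reproduce at the stated 0.80. It reproduces in all six cells if 0.85 is used instead (195.9 / (1 − P) = 280, 301, 327, 356, 392, 435), so the sensitivity value was carried into the specificity row.

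**Larger of the two, and what 500 gives.** Half-widths are 1.96 × √(0.1275 / (500P)) for sensitivity and 1.96 × √(0.16 / (500(1 − P))) for specificity. N is rounded to the nearest whole number, as in the protocol.

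| P | N(SN) | N(SP) printed | N(SP) at 0.80 | Larger, SP = 0.80 | Half-width SN, points | Half-width SP, points |
|---|---|---|---|---|---|---|
| 0.30 | 653 | 280 | 351 | 653 | 5.71 | 4.19 |
| 0.35 | 560 | 301 | 378 | 560 | 5.29 | 4.35 |
| 0.40 | 490 | 327 | 410 | 490 | 4.95 | 4.53 |
| 0.45 | 435 | 356 | 447 | 447 | 4.67 | 4.73 |
| 0.50 | 392 | 392 | 492 | 492 | 4.43 | 4.96 |
| 0.55 | 356 | 435 | 546 | 546 | 4.22 | 5.23 |

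**At the protocol's own incidences.**

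- 35%: 500 × 0.35 = 175 cases, the month-1 figure in the Stage II table, against 196 needed. This shortfall shows in the printed table and does not depend on the N(SP) error.
- 55%: 500 × 0.45 = 225 non-cases, against 246 needed. This shortfall appears only once N(SP) is computed at 0.80; the printed 435 conceals it.

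**Range in which 500 meets both limits.** Sensitivity needs P ≥ 195.9 / 500 = 0.392. Specificity needs P ≤ 1 − 245.9 / 500 = 0.508. Neither 0.35 nor 0.55 lies between them.

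**The case against.** The strongest reply is that the closing statement does not rest on the N(SN)/N(SP) table alone. It follows the accrual tables directly and speaks of a sufficient number of index events. The Stage II cumulative counts are 488 episodes and 907 non-episodes, well above 196 and 246. On that counting both limits are met.

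This does not resolve the point. The counts add the monthly figures (175 + 162 + 151 = 488; 325 + 302 + 280 = 907) and total 1,395, while the same table keeps cumulative patients at 500. The same people are counted again each month under a heading of unique patients. The totals would answer the point only if the patient-month were the unit and repeated months in one patient were independent. The section says neither.

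It is also fair to say that the study is described as observational and exploratory, that 12.1 calls such calculations less relevant to that design, that the primary outcome in section 6 is a correlation confidence level, and that the loss of precision is small. All of that stands, and it limits the weight of the point. It does not remove the inconsistency between two stated minimums and a size tied to one of them.

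A reader might go further and infer that the either/or rule can never fail, so that 500 would look sufficient whatever the incidence. The protocol does not support that. It makes the choice depend on priorities and does not say that the smaller figure is taken. Once a priority is named, the rule can fail: with sensitivity first, 653 and 560 exceed 500 at 0.30 and 0.35; with specificity first, 546 exceeds it at 0.55. Both rows are printed in full, including the cells above 500, so there is no sign that the smaller row was picked.

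**Conclusion.** The point holds in a limited form. Section 12.1 states two minimums with one precision but leaves open which of them sets N. With both required, N is the larger of the two, and 500 unique patients meet it only for incidences of about 0.39 to 0.51. At 35% sensitivity would be estimated to about 5.3 points, and at 55% specificity to about 5.2 points, instead of 5.0. The worst value on the grid is 5.7 points, at 30%. These are modest shortfalls in stated precision, not a reason to doubt that the study can be done.

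The conclusion assumes that both limits are meant as requirements, that W is a half-width, that the patient is the unit, and that P is the proportion of unique patients with an episode. If later months add new cases among the same 500 patients, cases rise but non-cases fall by the same number, so the final proportion must still lie between about 0.39 and 0.51. The figures use 500. The closing sentence of 12.1 gives 400 for the main stage, and at 400 the half-widths would be about 5.9 points for sensitivity at 35% and 5.8 for specificity at 55%.

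**What to change.** In section 12.1:

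1. Replace the either/or sentence with a statement that the required N is the larger of N(SN) and N(SP).
2. Recompute the N(SP) row with SP = 0.80: 351, 378, 410, 447, 492, 546.
3. Add the larger-of-two row: 653, 560, 490, 447, 492, 546. Built from the printed N(SP) row it would be wrong at 0.45, 0.50 and 0.55 (435, 392, 435).
4. State the sensitivity and specificity half-widths that 500 unique patients give at each incidence, including 35% and 55%. The worse of the two is 5.7, 5.3, 4.95, 4.7, 4.96 and 5.2 points across the grid.

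The cost is one sentence, one corrected row and a few added rows. Enrolment does not change. The stated precision becomes slightly less favourable at the ends of the grid.
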